6.2 Discussion of Study Design

This study is a single dose, sequential-dose escalation study in patients undergoing PCI due to ACS with NSTEMI. The first 2 doses were considered safe and well tolerated in the Phase 1 healthy subject study. The third dose to be given will be determined based on the safety and efficacy results from the first 2 doses. Dose escalation/de-escalation and stopping rules have been put in place to ensure the safety of the patients in this study (see Section 6.1).

The patients in this study will receive a single MT1002 close to the initiation of PCI (Day 1) followed by 4 hours of IV infusion and follow-up at Day 2, Day 14, and Day 30. This period is considered adequate for the collection of PK, efficacy, and safety data.

6.3 End of Study

A patient will have fulfilled the requirements for study completion if/when the patient has completed all study periods, including the end of study (EOS) visit or the last scheduled visit as indicated in the Schedule of Assessments (Table 4).

The end of the study will be the last patient's last visit as indicated in the Schedule of Assessments (Table 4).

7 SELECTION OF STUDY POPULATION

7.1 Inclusion Criteria

Individuals must meet all of the following criteria to be included in the study:

1. Males and females ≥ 18 to 85 years of age.
2. Diagnosed with NSTEMI defined as new or presumably new ST-segment depression of at least 1 mm in 2 contiguous leads, T-wave inversion more than 3 mm, or any dynamic ST shifts, or elevated troponin I (or troponin T if the local site does not have the troponin I test) higher than upper limit of normal (ULN), or CK-MB consistent with the universal definition of MI.
3. Patients who will undergo PCI during the index hospitalization for an NSTEMI (ideally patients start of PCI within 96 hours of presenting to the emergency room/ hospital).
4. Ability to understand and willing to give written informed consent. Signed informed consent form before any study related activities.
5. Women of childbearing potential (WOCBP) must have a negative pregnancy test or be post-menopausal for at least 1 year before enrollment or be permanently sterilized since ≥ 6 weeks (i.e., documented hysterectomy, bilateral salpingectomy, or bilateral oophorectomy). Females of childbearing potential and males with partners of childbearing potential must be using effective contraception if they become sexually active from the time of consent to 90 days after the MT1002 infusion day (i.e., any double combination of male or female condom with spermicidal gel, diaphragm, sponge, or cervical cap with spermicidal gel). Women who are breastfeeding are excluded. For the definition and list of allowed highly effective methods of contraception, see APPENDIX 1.

7.2 Exclusion Criteria

Individuals meeting any of the following criteria at Screening are ineligible to participate in this study:

1. Cardiogenic shock or prolonged cardiopulmonary resuscitation (CPR).
2. Active bleeding, bleeding diathesis, coagulopathy.
3. Any history of intracranial bleeding or structural abnormalities (intracerebral mass, aneurysm, arteriovenous malformation [AVM]).
4. Prior transient ischemic attack, prior stroke within 6 months.
5. Index MI is STEMI (ST elevation Myocardial Infraction).
6. The following planned procedures within 30 days after enrollment: CABG, valve surgery, or additional invasive procedures.
7. Requirement for oral anticoagulants before Day 7 post IP treatment.
8. Based on investigator's discretion, subject is at high bleeding risk, i.e., CRUSADE (Can Rapid risk stratification of Unstable angina patients Suppress ADverse outcomes with Early implementation of the American College of Cardiology/American Heart Association [ACC/AHA] Guidelines) bleeding risk score >60.
9. Suspected aortic dissection.
10. History of gastrointestinal or genitourinary bleeding within the previous 3 months.
11. Refusal to receive blood transfusion if needed during the study.
12. Major surgery in the last month.
13. History of heparin-induced thrombocytopenia and bleeding diathesis.
14. Severe uncontrolled hypertension, defined as a systolic blood pressure > 180 mmHg and diastolic blood pressure > 100 mmHg up to 24 hours of adequate treatment.
15. Prior (within 30 days prior to enrollment) or planned administration of thrombolytics, glycoprotein IIb/IIIa inhibitors, bivalirudin, or fondaparinux for the index MI. Subcutaneous injections of unfractionated heparin and low molecular weight heparin are allowed up to 4 hours and 8 hours, respectively, before study drug. Use of intravenous unfractionated heparin may be continued up until the time of enrollment (just prior to PCI), if ACT is < 200 seconds.
16. Known relevant hematological deviations: hemoglobin (male) < 11 g/dL hemoglobin (female) < 10 g/dL, hematocrit < 35%, platelet count < 100,000 cells/ μ L.
17. Use of Coumadin derivatives and/or Factor Xa inhibitor drugs within the last 7 days.

18. Chronic therapy with non-steroidal anti-inflammatory drugs (NSAIDs; except aspirin) (NSAID use is defined as chronic if these medications are taken more than three times a week for more than three months), cyclooxygenase (COX)-2 inhibitors within 1 month before screening.
19. Known malignancies or other comorbid conditions with life expectancy < 1 year that may result in protocol noncompliance.
20. Known severe liver disease (i.e., aspartate aminotransferase [AST], alanine aminotransferase [ALT] > 3 × ULN).
21. Known positive serology for hepatitis B & C, HIV screen.
22. Known chronic kidney disease with estimated glomerular filtration rate (eGFR) < 30 mL/min and/or dialysis.
23. Known allergy or intolerance to aspirin, clopidogrel, ticagrelor, prasugrel, bivalirudin, UFH, P2Y12 antagonists, or contrast.
24. Previous enrollment in this trial.
25. Inability to fully cooperate with the study protocol.
26. Any other medical or psychiatric condition that in the Investigator's judgment precludes participation in the study.

7.3 Study Withdrawal, Removal, and Replacement of Patients

If a patient discontinues study treatment and/or is withdrawn from the study for any reason, the study site must immediately notify the Medical Monitor. The date and the reason for treatment/study discontinuation must be recorded on the electronic case report form (eCRF). Patients who complete or discontinue early from the study will be asked to return to the study site within 30 days of completion of PCI to complete assessments as indicated in the Schedule of Assessments (Table 4).

In the event that a patient discontinues prematurely from the study because of a treatment-emergent AE (TEAE) or serious TEAE, the TEAE or serious TEAE will be followed up until it resolves (returns to normal or baseline values) or stabilizes, or until it is judged by the Investigator to no longer be clinically significant.

Patients who are enrolled but do not undergo PCI (e.g., because of PCI contraindication or exclusion criteria revealed after coronary angiography) will be replaced for the study.

- Patients who drop out during the screening phase before enrollment with MT1002 dose allocation will be considered a screen failure. They are to be recorded as screen failures in the eCRFs, along with the reason for failing screening, and no further follow-up is required.
- Patients who discontinue treatment prematurely, and/or discontinue or withdraw from the study after enrollment with MT1002 dose allocation will be considered as “early

discontinuations” and the reason for premature discontinuation must be recorded in the eCRFs. The data will be included in the trial database and will be reported.

Once a patient is withdrawn from the study, the patient cannot reenter the study.

A patient may voluntarily withdraw or be withdrawn from the study at any time for reasons including, but not limited to, the following:

- unacceptable toxicity or AE
- patient withdrawal of consent: at any time, a patient’s participation in the study may be terminated at his/her request or on the basis of the Investigator’s clinical judgment. The reason for patient/subject withdrawal will be noted on the eCRF.
- intercurrent illness: a condition, injury, or disease unrelated to the primary diagnosis that becomes apparent during treatment and necessitates the patient’s termination from the study
- general or specific changes in the patient’s condition that renders him/her ineligible for further treatment according to the inclusion/exclusion criteria
- patient fails to adhere to the protocol requirements (e.g., failure to return for defined number of visits)
- lost to follow-up: the patient stops coming for visits, and study personnel are unable to contact the patient

Additionally, the Sponsor may stop the study at any time for safety, regulatory, legal, or other reasons aligned with good clinical practice (GCP). This study may be terminated at the discretion of the Sponsor or any regulatory agency. An Investigator may elect to discontinue or stop the study at his or her study site for any reason, including safety or low enrollment.

As this is a single-dose study in which the treatment period starts before PCI and continuation in the study consists of standard of care collection of medical outcomes, the Investigators are encouraged to continue collection of medical information to ensure patient safety, and all patients will be asked to allow information from their medical records (including non-study-related records) to continue to be collected through 30 days post-dose.

8 TREATMENTS

8.1 Details of MT1002

MT1002 is a white or off-white amorphous powder that is highly soluble in water. The MT1002 dosage form was designed based on the physical and chemical properties of MT1002. Because MT1002 is a peptide, it is not stable in solution. Therefore, a lyophilized product for injection is developed. Mannitol is used as an excipient. The compatibility study of the active pharmaceutical ingredient and excipient shows that mannitol has no impact on the stability of the active pharmaceutical ingredient.

MT1002 is provided as a solution for injection filled in a transparent tubing borosilicate glass vial (Type 1, US Pharmacopeia) stopped with a brominate butyl rubber stopper and capped with a combined aluminum-plastic cap. Each vial contains 50 mg of MT1002. The composition of a MT1002 50 mg/vial is provided in Table 2.

Table 2 Composition of MT1002 for Injection, 50 mg/vial

Components	Unit Formula (50 mg)	Quality Reference	Function
MT1002	50.0 mg	In-house	Active pharmaceutical ingredient
Mannitol	90 mg	USP/NF	Excipient
Sodium hydroxide	Sufficient quantity	USP/NF	Adjust pH
Water for injection	Add to 2 mL	USP	Solvent

Abbreviations: NF, National Formulary; USP, United States Pharmacopeia.

Results from stability studies demonstrate that MT1002 for injection remained chemically and physically stable during 6 months of storage at accelerated condition ($25\pm 2^{\circ}\text{C}/60\%\pm 10\%$ relative humidity) and 12 months at long-term stability conditions ($5\pm 3^{\circ}\text{C}$).

All drug supplies will be provided by the Sponsor.

8.2 Dosage Schedule

Patients will receive MT1002 IV followed by MT1002 infusion for 4 hours. This regimen was found safe and well tolerated in Phase 1. MT1002 will be initiated as close to the start of PCI as possible. MT1002 should be initiated during diagnostics angiography when indication for PCI is confirmed, provided the early PCI is indicated right after the coronary angiography. PCI can start after MT1002 initiation as soon as ACT is confirmed to be ≥ 200 sec or within 30 min after MT1002 starts, whichever occurs first. MT1002 will be administered by an intravenous injection of 0.90 mg/kg, 1.2 mg/kg, 0.75 mg/kg or 0.6 mg/kg (depending on the dose selected for the cohort) via IV access prior to the PCI procedure, immediately followed by an IV infusion of 1.8 mg/kg/hour, 2.3 mg/kg/hour, 1.6 mg/kg/hour or 1.2 mg/kg/hour (depending on the dose selected for the cohort) until completion of the procedure.

Patients will be discharged from the hospital when they are stable, as defined by the Investigator's judgment. Patients will be followed for 30 days from study drug dosing.

Three doses of MT1002 will be evaluated in this study as noted in the table below. The first dose level is 0.90 mg/kg initial loading dose (bolus intravenous injection) + 1.8 mg/kg/h (infusion) for 4 hours. The second dose level will be based on the results from the first cohort (If the dose is escalated, then the second dose level is 1.2 mg/kg initial loading dose (bolus intravenous injection) + 2.3 mg/kg/h (infusion) for 4 hours; if the dose is de-escalated, then the second dose level is 0.6 mg/kg initial loading dose (bolus intravenous injection) + 1.2 mg/kg/h (infusion) for 4 hours). The third dose will be based on the results from the initial 2 cohorts (Table 3). The goal is to achieve a target ACT of 200 to 300 sec (within 30 minutes after infusion initiation) during the continuous infusion period of MT1002.

Patients who are enrolled but do not undergo PCI (e.g., because of PCI contraindication revealed after coronary angiography or due to exclusion criteria) will be replaced for the study. However, the patients will be evaluated as safety population.

Dose adjustment guideline for cohort 3 dosing regimen is below. All adjustment will be documented in the patient's source document in detail:

- Bolus and maintenance dosing

All patients will receive 0.75 mg/kg as an IV bolus dose, followed immediately by 1.6 mg/kg/hr*4h IV for the duration of the PCI. Five minutes after the bolus dose, ACT should be performed and an additional bolus of 0.3 mg/kg IV may be given if needed (i.e., ACT <200 sec).

- Dosing during infusion period

10 minutes after initiation of 1.6 mg/kg/hr IV for the duration of the PCI, or 5 minutes after additional bolus if it is given, additional ACT can be monitored, and IP infusion rate can be adjusted. An incremental 10% additional infusion rate can be titrated up until ACT >200 sec. If ACT >300 sec during that period of time, IP infusion can be stopped for 5 minutes, and/or the rate of infusion can be adjusted until ACT maintains between 200 sec and 300 sec. Duration of IP infusion can be 4 hours +/-30 minutes in order to accommodate potential infusion rate adjustments.

Table 3 Planned Dose Regimen of MT1002 for Injection and Expected ACT and aPTT Values

Sequence	N	MT1002: Initial loading dose and maintenance dose	Expected peak ACT based on Phase 1 results in healthy volunteers	Expected peak aPTT based on Phase 1 results in healthy volunteers	Expected ACT in 5 min after MT1002 start	Expected aPTT in 5 min after MT1002 start	Expected ACT in 30 min after MT1002 start	Expected aPTT in 30 min after MT1002 start
First dose cohort	6	0.90 mg/kg + 1.8 mg/kg/h*4h	234.3±26.1 sec – at 4 hours	74.4±6.2 sec – at 4 hours	209.7±19.2	63±4.8	212.3±29.5	65.6±7.5
Second cohort if dose escalated	6	1.2 mg/kg + 2.3mg/kg/h*4h	253.8±9.6 sec – at 2 hours	83.6±5.4 sec – at 4 hours	234.3±6.9	74.5±7.3	240.3±4.1	78.3±9
Second cohort if dose de-escalated	6	0.60 mg/kg + 1.2 mg/kg/h*4h	221.7±11.1 sec – at 2 hours	65.9±2.5 sec – at 4 hours	194.5±28.6	56.5±7.4	216.2±15.7	60.6±4.4
Third expansion cohort	6-8	0.75 mg/kg + 1.6 mg/kg/h*4h based on results from initial 2 cohorts	220.7 sec at 4 hours	67.7 sec at 4 hours	217.5	66.5	216.5	66.1

Abbreviations: ACT, activated clotting time; aPTT, activated partial thromboplastin time; h, hours; min, minutes; N, number of patients; sec, seconds; Tbd, to be determined.

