Follow-up: At completion of PCI, subjects will be continued on IV MT1002 for 4 hours from infusion start. All patients will stay on clopidogrel 75 mg/day. If the local clinical guidance recommends use of Ticagrelor or Prasugrel, the recommended maintenance doses will be: Ticagrelor 90 mg twice daily or Prasugrel 5-10 mg daily and aspirin 75-100 mg/day (according to local countries clinical practice guidance) and be followed up for 30 days. Longer-term follow-on treatment will be done according to local treatment guidelines outside of this protocol.

Rescue: Patients who fail to achieve an ACT target of 200 to 300 sec with MT1002 (within 30 minutes after MT1002 infusion initiation) will be switched to standard of care (unfractionated heparin [UFH] or bivalirudin) and discontinued from the study drug.

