- Administer study drug via IV access before the PCI and record time of dosing in the eCRF. Study drug should be administered in catheterization lab as close to randomization and the start of the PCI procedure as possible.
- Conduct a visual bleeding inspection and assess bleeding AEs according to the BARC criteria; record any patient-reported bleeding.
- Record any other AEs that have occurred.

9.2.3 During Percutaneous Coronary Intervention, Day 1

Either radial access/distal radial access PCI or femoral access PCI will be used in this study. It is up to the discretion of the Principal Investigator what type of stent(s) will be used.

- Conduct the PCI procedure per local standard of care.
- Record TIMI flow grade post PCI.
- Patients who fail to achieve ACT target of 200 to 300 sec with MT1002 (within 30 minutes after MT1002 infusion initiation) before PCI will be switched to standard of care (UFH or bivalirudin, see Section 8.5.1).
- Patients who achieve ACT target of 200 to 300 sec with MT1002 (within 30 minutes after MT1002 infusion initiation) before PCI should continue the study drug infusion for 4 ± 0.5 hours after infusion start.
- Monitor patients for potential AEs, including allergic reactions during the MT1002 administration.
- Record vital signs (body temperature, respiration rate, heart rate, and systolic and diastolic blood pressure).
- Record any procedural complications, as well as any other AEs
 - Glycoprotein IIb/IIIa inhibitors may be used for procedural or angiographic complications only (dosing per local standard of care, see Section 8.5.1)
 - In those patients who experience significant intracoronary thrombosis during the procedure, or experience acute thrombosis after the procedure, heparin bail out may be administered (see Section 8.5.1).
- Perform a PA (by PFA100 or PFA200) according to the time points in the Schedule of Assessments (Table 4) and Table 5.

- Obtain central cardiac biomarkers (troponin I [troponin T can be measured if the local site does not have the troponin I test], and CK-MB) according to the time points in the Schedule of Assessments (Table 4) and Table 5.
- Obtain coagulogram (ACT, aPTT, PT, TT, FIB, INR according to the time points in the Schedule of Assessments [Table 4] and Table 5), hemoglobin, hematocrit, platelet count, RBC, and WBC counts.
- Obtain PK samples according to the time points in the Schedule of Assessments (Table 4) and Table 5.

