- Conduct a visual bleeding inspection and assess bleeding AEs according to the BARC criteria; record any patient-reported bleeding.
- Record all changes in concomitant medications.
- Obtain a copy of the PCI procedure report and record information about index-procedure (e.g., but not limited to vascular access, lesions treated, stents used, procedure result). Successful treatment with PCI is defined as achievement of < 30% residual diameter stenosis of all treated lesions assessed by visual inspection or quantitative coronary angiography, without an in-hospital major adverse cardiac event (death, MI or repeat coronary revascularization of the target lesion).

9.2.4 Post Percutaneous Coronary Intervention, Day 1

- Record end of PCI time in the eCRF. End of procedure is defined as the date/time when the last coronary catheter (all catheters other than arterial sheath or intra-aortic balloon positioning) is removed from the body.
- Continue MT1002 infusion for 4 hours after infusion start (including post-PCI).
- Remove the sheath approximately 3 hours after MT1002 infusion is complete. Record sheath removal time in the eCRF.
- Perform a brief physical examination.
- Record vital signs (body temperature, respiration rate, heart rate, and systolic and diastolic blood pressure).
- Perform a 12-lead ECG.
- Perform a PA (by PFA100 or PFA200) according to the time points in the Schedule of Assessments (Table 4) and Table 5.
- Collect blood samples for hematology, coagulogram, and cardiac biomarkers (refer to Section 11.5 for parameters included)
 - CK-MB, cardiac troponin I (troponin T can be measured if the local site does not have the troponin I test) according to the time points in the Schedule of Assessments (Table 4) and Table 5
 - ACT, aPTT, PT, TT, FIB, INR as per time points in the Schedule of Assessments (Table 4) and Table 5
 - Hematocrit, hemoglobin, platelet count, RBC and WBC counts according to the time points in the Schedule of Assessments (Table 4)

This document is confidential.

- Obtain PK samples according to the time points in the Schedule of Assessments (Table 4) and Table 5.
- Record all changes in concomitant medications.
- Conduct a visual bleeding inspection and assess bleeding AEs according to the BARC criteria; record any patient-reported bleeding
 - Immediately upon achievement of hemostasis, with time of complete hemostasis recorded on the eCRF;
 - Thereafter, per local standard of care
- Record any other AEs that have occurred.

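### Section 8.2 contradicts itself and the rest of the protocol on when the MT1002 infusion ends: completion of the PCI, or 4 hours from infusion start

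*Combined protocol and SAP*

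**What the plan says.** **Text that ends the infusion with the procedure.** Section 8.2 gives the four infusion rates and then says "depending on the dose selected for the cohort) until completion of the procedure". The Cohort 3 guideline in 8.2, repeated in the synopsis, carries both durations in one phrase: "followed immediately by 1.6 mg/kg/hr*4h IV for the duration of the PCI". Its next bullet again attaches the PCI duration to the infusion.

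**Text that runs it for 4 hours.**
- Section 8.2 opens with "Patients will receive MT1002 IV followed by MT1002 infusion for 4 hours" and labels the dose levels the same way: "The first dose level is 0.90 mg/kg initial loading dose (bolus intravenous injection) + 1.8 mg/kg/h (infusion) for 4 hours". Table 3 carries a 4-hour label for every regimen.
- Section 6.1: "At completion of PCI, subjects will be continued on IV MT1002 for 4 hours from infusion start".
- Section 9.2.3, for patients who reach target ACT: "should continue the study drug infusion for 4 ± 0.5 hours after infusion start".
- Section 9.2.4: "Continue MT1002 infusion for 4 hours after infusion start (including post-PCI".
- The Cohort 3 guideline also has a window: "Duration of IP infusion can be 4 hours +/-30 minutes".

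**A third anchor.** The Treatment Duration row of the synopsis has treatment lasting roughly four hours counted from enrollment, not from infusion start.

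All of this is current text. No order of precedence is given.

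**The concern.** Section 9.2.4 defines the end of the procedure by removal of the last coronary catheter and expects the infusion to carry on afterwards. By the protocol's own account, then, PCI normally ends before four hours, and the two instructions are different treatments.

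The primary objective is to identify a safe and well tolerated dose, and each cohort of about six is named by a 4-hour regimen. A site following the clause in 8.2 would deliver less drug under the same label. Section 14 summarises by cohort everyone who received at least one dose. It describes no summary by dose received, so mixed exposure would not show in the tables.

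Several later items assume an infusion still running, or are timed from its end:
- Table 5 places the 4-hour sample five to ten minutes before the infusion finishes.
- Table 3 expects peak ACT at 2 or 4 hours.
- Section 9.2.4 times sheath removal at about 3 hours after the infusion is complete.
- Section 8.5.1 restricts heparin, with listed exceptions, until 7 hours after completion.

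**Working it through.** **1. What a regimen label means.** Section 4.2.2 converts the Phase 1 starting regimen, 0.15 mg/kg + 0.3 mg/kg/h for 4 h at 70 kg, to 94.5 mg. Check: (0.15 + 0.3 × 4) × 70 = 94.5 mg. This matches exactly, so a label means the bolus plus four full hours.

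**2. Dose delivered if the infusion stops T hours after it starts.**
Delivered = bolus + rate × T. Labelled = bolus + rate × 4. Fraction = delivered / labelled.

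Bolus and rate come from Table 3. T is an assumption, because the documents give no PCI duration. T is counted from infusion start, not from the start of PCI. Section 8.2 lets PCI begin up to 30 minutes after MT1002 starts, so a PCI of 0.5 to 2 h corresponds to T of roughly 0.5 to 2.5 h.

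| Regimen (mg/kg + mg/kg/h) | Labelled mg/kg | T = 0.5 h | T = 1 h | T = 2 h | T = 2.5 h |
|---|---|---|---|---|---|
| 0.90 + 1.8 | 8.10 | 1.80 (22.2%) | 2.70 (33.3%) | 4.50 (55.6%) | 5.40 (66.7%) |
| 1.2 + 2.3 | 10.40 | 2.35 (22.6%) | 3.50 (33.7%) | 5.80 (55.8%) | 6.95 (66.8%) |
| 0.60 + 1.2 | 5.40 | 1.20 (22.2%) | 1.80 (33.3%) | 3.00 (55.6%) | 3.60 (66.7%) |
| 0.75 + 1.6 | 7.15 | 1.55 (21.7%) | 2.35 (32.9%) | 3.95 (55.2%) | 4.75 (66.4%) |

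For scale, the 4 h ± 30 min window at a constant rate moves the first regimen only to 7.2/8.1 = 88.9% or 9.0/8.1 = 111.1%. At T = 2.5 h, the 0.90 + 1.8 regimen delivers 5.40 mg/kg, which is the labelled total of the 0.60 + 1.2 regimen.

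**3. Which measurements depend on the end point.**
- *ACT at 5 and 30 minutes:* unaffected unless the procedure ends first.
- *4-hour ACT and PK:* drawn 4 − T hours off drug, so 3.5, 3, 2 or 1.5 h for the values of T above.
- *Peak ACT above 300:* Table 1 separates at most 2/6 from at least 3/6, so one patient can change the decision. A peak that would come at 2 or 4 h might not occur if the infusion had stopped.
- *ACT below 200 in Cohort 2:* Section 6.1 counts patients with at least one such value and gives no time limit. If the Study Management Group counts readings up to the nominal end of infusion, a 4-hour reading taken off drug could add to the count.
- *Sheath and heparin times:* with a 4-hour infusion these fall about 4 + 3 = 7 h and 4 + 7 = 11 h after infusion start. With T = 1 h they fall at about 4 h and 8 h.

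**The case against.** The case for treating this as a drafting slip is strong. Most of the text says 4 hours, including 8.2's own first sentence and dose labels. Sections 6.1 and 9.2.4 address exactly what happens when PCI finishes, and the visit procedures that staff follow in 9.2.3 and 9.2.4 are clear. Many sites would probably run four hours. The ACT co-primary endpoint concerns the time before and during PCI, when the infusion is running on either reading. The version 6.0 change summary reports Cohort 1 peaks above 300 at 5 minutes in three patients and at 30 minutes in one, which are early time points. Cohort 3 is titrated individually, analyses are descriptive, and Section 8.4 already requires timing and dose to be recorded.

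All of that stands, and it limits the point. It does not remove a contrary instruction from the section headed Dosage Schedule, and the Cohort 3 guideline carries the same conflict. Recording early termination is only a partial safeguard: under the clause in 8.2, an infusion stopped with the PCI would count as complete.

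A reader might infer that patients received about a third of their labelled dose, or that cohorts in fact mix exposures. The documents do not support this. One third applies only if the infusion stops about 1 hour after it starts, and nothing shows that any site did so. Nor can the drug level remaining at 4 hours be calculated: elimination in humans is described only as fast, with no half-life given.

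**Conclusion.** The contradiction is real, lies in current text and is unresolved. It is partly internal to 8.2, not simply 8.2 against other sections. Following the minority wording would cut the delivered dose to about 22% to 67% of label for stops between 0.5 and 2.5 hours after infusion start. That range rests on assumed stop times, a constant rate and no extra bolus.

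The consequences are confined to the 4-hour ACT and PK sample, later ACT peaks and lows that feed the cohort rules, bleeding after PCI, and the two windows timed from infusion completion. Early ACT readings and the ACT co-primary are largely untouched. Because the instruction defines the treatment under test and the correction is cheap, it should be corrected rather than left to site interpretation. This review takes no position on which end point is right.

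**What to change.** 1. Reconcile the text so that one infusion end point holds throughout, with the clinical team deciding which. Six places need attention against 6.1, 9.2.3 and 9.2.4: the clause in 8.2, two phrases in the 8.2 Cohort 3 guideline, the same two in the synopsis, and the enrollment-based duration in the synopsis.
2. Before cohorts are compared, list for each patient the actual infusion start and stop times and the total mg/kg received. Flag anyone whose duration departs from the reconciled rule. Section 8.4 already records timing, duration and dose. It places duration in the medical file, so confirm that the stop time reaches the eCRF. For Cohort 3, confirm that the adjustments held in source documents do too.

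The cost is a few sentences of protocol text, one listing and one derived variable in the SAP. No additional patients or samples are needed.
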